AIM 1. Integrate evidence-based components of “*Activate for Life*” a telehealth delivered, nurse-led behavioral health program for low income older adults targeting pain and fatigue through balance training (Otago), strengthening and mindfulness (Yoga), and affective state (Behavioral Activation).

We hypothesize that the evidence-based Otago and Yoga components of this intervention will integrate with the ‘infrastructure’ format of the Behavioral Activation mental health treatment insofar as a 60-minute session, 6-10 session intervention will be developed.

Aim 2. Test the feasibility of Activate for Life in terms of its individual components by comparing Otago vs. Otago+Yoga vs. Otago+Yoga+Behavioral Activation in a pilot RCT design with 10 participants in each of the 3 conditions in terms of recruitment, intervention ‘dosage’ (frequency/density), adherence, treatment satisfaction, attrition, rates of missing data, and other feasibility metrics, including qualitative feedback from participants for final intervention refinement.

We hypothesize that adherence will be adequate (65% scheduled activity compliance), satisfaction will be high (above 80%), attrition will be limited (below 25%), and followup data collected (below 20% missing data)

AIM 3. Determine an initial efficacy signal for the intervention that will inform future power estimates.

We hypothesize that the combined intervention will show significant within subject improvement over baseline on measures of pain, fatigue, and depression.

Supplemental ARM 4 - AIM 4. Test the feasibility of a 12-week e/mHealth gentle yoga+yogic breathing (GYYB) intervention for alleviating symptoms of burden in aging Caregivers (CG) of persons (N=20) with dementia (PWD); measure initial changes in stress and QoL indicators in CG and PWD (post- vs. pre-intervention).

Impact. This pilot feasibility study will set the stage for a full scale RCT demonstrating the additive benefit (if present) of each additional component over the CDC approved balance intervention Otago. Self-management of pain and fatigue through strength and balance training in low-income older adults can improve quality of life, decrease health care costs, and increase the ability of the person with these symptoms to age in place.

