3.0 Intervention to be studied

ARMS 1, 2, and 3. Design Overview. Design Overview and Project Timeline:

This 12-week feasibility trial will use a 3x3 repeated measures (treatment x time) between groups randomized trial design to compare Otago (OG) vs. Otago + Yoga (GYB) vs. Otago + GYB + Behavioral Activation (ie., the complete *Activate for Life* intervention) in low-income older adults with chronic pain and/or fatigue at baseline, post-treatment and 3- month follow-up. Participants will be randomly assigned to one of the three conditions. Daily self-monitoring of program component adherence, PROMIS self-report measures of pain, fatigue, anxiety, depression, and social support. Physical activity measures will include actigraphy, steps per day, 2-minute timed walk test, sit-to-stand test, and Mini-Best. Participants will be 30 adults (10 per group) age 60 and above with a PROMIS pain interference score of eight or above and/or a PROMIS pain behavior score of 15 or above (cut points based on a T-score that rescales the raw score into a standardized score with a mean of 50 and a standard deviation (SD) of 10 for each of these instruments).

Alternative design: The progressive nature of this feasibility trial allows the proven evidence-based modalities of OEP and GYB to be combined with behavioral activation to not only address physical activity but also the mental health aspects of chronic pain and fatigue. Therefore, this feasibility trial scaffolds the components to show that the modalities of OEP and GYB are effective and their success is dependent on motivation. However, we are not testing these three interventions alone, or in every possible combination.

Supplemental ARM 4 - Design Overview:

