Fatigue Lower extremity strength Balance and Function Walking capacity	30 Second Chair Stand Test (not determined) ⁴² Mini Balance Evaluation Systems Test (MiniBEST) (0.91) ⁴³ Two Minute Walk Test (0.82) ⁴⁴	Baseline; Study end Baseline; Study end Baseline; Study end
Self-report measures Function Depression Social support Self-efficacy	PROMIS Physical Function (0.95) ⁴⁵ PROMIS Depression Short Form 8a (0.95) ⁴⁶ Revised UCLA Loneliness Scale (0.94) ⁴⁷ Pain Self-Efficacy Scale (0.93) ⁴⁸	Baseline; Study end Baseline; Study end Baseline; Study end Baseline; Study end
Adoption Adherence	Participation in weekly self-management telehealth visits; frequency of participation in Otago and/or Yoga as recorded in participant diary and data from activity tracker; frequency of use of self-management techniques as recorded in participant diary; # of patients who successfully complete self-management program; # of and reasons for dropouts	Tracking forms; weekly review of participant diary; weekly assessment of feedback; end of study participant interviews and satisfaction questionnaires
Acceptability		

Endorsement	Usability of tablet technology and activity tracker; # and types of problems encountered; participant satisfaction with self-management program and technology	Assess at weekly team meetings; acceptability checklist and tracking forms; end of study participant interviews and satisfaction questionnaires
Implementation		
Technology	# of problems encountered with tablet, activity tracker, vital sign equipment; # and types of problems encountered with study setup; was fidelity to training protocol maintained; was orientation completed as planned; was standardized checklist used to instruct participants; assessment of participant for suggestions; # of changes made to intervention based on suggestions	Tracking forms; weekly team meetings; end of study participant interviews and satisfaction questionnaires
Site set up		
Consistency of intervention		
Maintenance		
Projection of future adoption	# patients who would continue intervention; potential for future applications	End of study participant interviews and satisfaction questionnaires

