Official title: Activate For Life: mHealth Intervention To Address Pain And Fatigue In Lowincome Older Adults Aging In Place

NCT03853148

Document date: 03/12/2021

Analysis plan

Data were analyzed using IBM SPSS Version 26.0. Mean substitution was conducted to account for missing data (these did not represent more than 40% of overall dead data). Repeated measures analysis of variance (ANOVA) was used to determine significant differences for outcome variables between the 3 intervention Arms. Differences were considered statistically significant for *p*-values <0.05. Analyses were similar for outcomes in the caregiver group.

Measures of feasibility including recruitment and reach, fidelity and adherence, formal satisfaction, and drop-out proportions were evaluated. Then 95% confidence intervals for proportions were used to estimate dichotomous outcomes (e.g., the proportion of subjects who: agree to participate out of the number that are approached, the proportion who complete the intervention, the proportion who report satisfaction with the intervention, and the proportion who exit the study prematurely [drop out]). Further, the participants' reasons for drop out, and problems/issues encountered with the intervention were described via frequency distributions. For continuous measures (e.g. satisfaction scores), frequency distributions and the median and mean responses (with 95% confidence intervals) were obtained. Univariate descriptive statistics and frequency distributions were calculated as appropriate for all variables. Demographic variables obtained at baseline were described via measures of central tendency (mean, median), variability and frequency distributions as appropriate. Additionally, characteristics for those who were eligible for study versus those who were not eligible and for those who adhered to the study protocol (study completers) versus those who did not adhere (non-adherers and drop-outs) were compared to better describe the population for this study.

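### The SAP does not say which repeated measures ANOVA term is the treatment comparison; read literally, it is an arm effect that averages in the pre-treatment baseline

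*SAP*

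**What the plan says.** The SAP's analysis plan contains the only between-arm efficacy test in either document: "Repeated measures analysis of variance (ANOVA) was used to determine significant differences for outcome variables between the 3 intervention Arms". The criterion is "Differences were considered statistically significant for *p*-values <0.05". The SAP names no F term, contrast, visit or role for baseline.

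Protocol 3.0 describes the design as a "3x3 repeated measures (treatment x time) between groups randomized trial design", with measurements "at baseline, post-treatment and 3- month follow-up". Table 2 in Protocol 10.0 gives most outcomes the schedule "Baseline; Study end", which is two occasions rather than three. Protocol 1.0 (Aim 2) plans "10 participants in each of the 3 conditions". The data analysis plan in Protocol 12.0 covers feasibility and description and has no between-arm efficacy test. The Aim 3 hypothesis in Protocol 1.0 is improvement over baseline within the combined arm.

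**The concern.** A repeated measures ANOVA with arm as a factor yields two different F tests involving arm. The arm main effect compares each participant's average over all visits. The arm x time term asks whether the arms change differently. A treatment x time design poses the second question, but the SAP's wording, taken literally, points to the first.

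If baseline is among the repeated measures, the main effect mixes a visit that treatment cannot have influenced into the quantity being compared. It also leaves between-person variance in the error term. Two consequences follow. A real difference in change may be missed although the same output would show it on another line. And with 10 per arm, a chance difference already present at baseline can carry through and be reported as a difference between arms. Aim 3 is meant to inform power estimates for the next trial, so a misread signal would carry forward.

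**Working it through.** **Inputs from the documents.** Three arms, n = 10 per arm (Protocol 1.0); alpha 0.05 (SAP); k = 2 visits (Protocol 10.0, Table 2) or k = 3 (Protocol 3.0). The documents give no power, effect size, SD or between-visit correlation, so there is no figure of the plan's own to reproduce.

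**Assumptions.** SD 1 at every visit; compound symmetry with correlation rho; equal expected baseline means (randomisation); post-baseline arm means 0, d/2, d; effect sustained when there are three visits; complete data (the SAP's mean substitution is not modelled).

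**Dilution.** Averaged over visits, a post-baseline difference d becomes (0 + d)/2 = d/2 with two visits and (0 + d + d)/3 = 2d/3 with three.

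**Noncentrality.** Let S be the sum of squared deviations of the post-baseline arm means: (d/2)² + 0 + (d/2)² = d²/2, or 0.5 at d = 1.

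- Arm main effect: lambda = n·S·c² / [(1 + (k−1)rho)/k], with c = 1/2 or 2/3; df 2 and 27.
- Arm x time, two visits: lambda = n·S·(1/2)/(1 − rho); df 2 and 27.
- Arm x time, three visits: lambda = n·S·(2/3)/(1 − rho); df 4 and 54.

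Example, two visits, d = 1, rho 0.5: arm effect 10 × 0.5 × 0.25 / 0.75 = 1.67; arm x time 10 × 0.5 × 0.5 / 0.5 = 5.00. The noncentral F gives 18% and 46% power.

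**Power at d = 1 SD, 10 per arm (arm effect → arm x time)**

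| rho | Two visits | Three visits, sustained |
|---|---|---|
| 0 | 25% → 25% | 58% → 25% |
| 0.3 | 20% → 34% | 39% → 35% |
| 0.5 | 18% → 46% | 32% → 48% |
| 0.7 | 16% → 68% | 27% → 72% |
| 0.8 | 15% → 86% | 25% → 90% |

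Five settings, including one with no treatment effect, were simulated with 20,000 runs each and agreed with the formulas to within 0.5 points.

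**Why visit number matters.** The ratio of noncentralities, arm effect to arm x time, is (1 − rho)/(1 + rho) with two visits. This never exceeds 1 for rho of 0 or more, and the degrees of freedom are equal, so arm x time is never the weaker test there. With three visits and a sustained effect the ratio is 2(1 − rho)/(1 + 2rho), which exceeds 1 below rho 0.25. The interaction also spends 4 df, so the arm effect remains ahead up to about rho 0.3.

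**Other settings.**
- At d = 1.2 and rho 0.5, 0.6, 0.7: two visits 24, 23, 22% against 62, 72, 84%; three visits 44, 41, 38% against 65, 76, 88%.
- At d = 2, rho 0.5, three visits: 88% against 99%.
- With 8 per arm (attrition below the protocol's 25% limit), two visits, d = 1, rho 0.5: 15% against 37%.

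**Baseline-adjusted alternative.** For one post-baseline visit with baseline as covariate, lambda is about n·S/(1 − rho²), df 2 and 26, ignoring the small cost of estimating the slope. At d = 1 and rho 0.3, 0.5, 0.7, 0.8 power is about 49, 58, 76 and 89%. Against the three-visit interaction (35, 48, 72, 90%) this is higher up to rho 0.7 and about equal at 0.8.

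**No treatment effect (simulation, 100,000 trials per setting, rho 0.5 to 0.8).** Both tests reject about 5% overall. When baseline happens to differ between arms at p < 0.20, the arm effect rejects 20 to 25% of the time and arm x time 6.5 to 10.5%. Such an imbalance is present in 81 to 98% of the arm effect's false rejections, against 26 to 43% for arm x time.

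**The case against.** The strongest reply is that the literal reading may not be what was done. A difference between arms is ordinary shorthand for a treatment comparison, and Protocol 3.0 already names treatment x time as the design. The SAP adds that caregiver outcomes were analysed similarly. That group is a single arm measured twice, so a similar ANOVA there can only give a time effect, which tells against a plan that looks only at the between-subjects line. This stands: the documents do not show that the arm main effect was used, only that the deciding term is unstated.

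A reader might infer that the plan loses 20 to 70 points of power whenever the effect is 1 SD or more. The documents supply none of the quantities needed for that statement. With three visits and low correlation the sign reverses, and at very large effects both tests approach 100%. Nor would the arm effect necessarily miss most large differences: with three visits it has 52 to 64% power at d = 1.5 and 78 to 88% at d = 2 (rho 0.5 to 0.8).

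A reader might also infer inflated false positives. Randomisation equalises baseline in expectation, so overall type I error is 5% for either test, and arm x time is not immune to baseline imbalance, only less affected.

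It is also fair that this is a 30-person feasibility trial whose stated efficacy hypothesis is within-subject. Between-arm power is therefore secondary. It still matters, because Protocol 1.0 looks ahead to a full-scale trial of each component's added benefit, which depends on between-arm differences in change.

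**Conclusion.** The point holds as an unspecified treatment comparison whose literal reading does not fit the design. If the arm main effect was read with baseline included, a treatment difference is halved (two visits) or cut by a third (three visits, sustained effect), and the result is more exposed to chance baseline imbalance. Overall type I error is not affected.

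The size depends on assumptions that the documents do not settle. With 10 per arm, arm means 0, d/2, d, compound symmetry and d = 1 SD, the two-visit loss is 14 to 70 points over rho 0.3 to 0.8. With three visits and a sustained effect, the range is from a 4-point advantage for the arm effect at rho 0.3 (33 points at rho 0) to a 64-point loss at rho 0.8. The two-visit case fits Table 2's schedule for most outcomes; the three-visit case fits Protocol 3.0. No single power-loss figure can be attached to the plan. The sponsor should correct this, but it does not undermine the feasibility aims.

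**What to change.** Amend the SAP sentence along these lines: *The treatment comparison is the between-arm difference in change from baseline. For outcomes measured at baseline and study end it is the arm x time term, or an arm comparison at a stated post-baseline visit with baseline as covariate. The arm main effect averaged over visits including baseline is not taken as evidence of a treatment difference.*

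If three visits are analysed, the baseline-adjusted comparison at a named visit is preferable to the 4-df interaction, for the power reasons shown above. The SAP should also say whether baseline enters as an outcome or a covariate, and Protocol 3.0 and Table 2 should be reconciled on the number of visits.

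The SAP is written in the past tense, so any result already read from the arm main effect should be re-reported from the chosen comparison.

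The cost is a few sentences. Arm x time is already in the output if the ANOVA included arm and time; the baseline-adjusted version is one further model on the same data. No new participants or measurements are needed. A difference already called significant might have to be withdrawn.
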